**NCT n° 03833765**

**November 28th 2012**

## INTRODUCTION

In patients with a sufficient amount ( $\geq 2\text{mm}$ ) of keratinized tissue, the Coronally Advanced Flap (CAF) has been demonstrated to be very effective in treatment of single (Linee Guida) and multiple recessions with advantages also in terms of aesthetics and morbidity (Chambrone et al. 2018, Pini Prato et al. 2014). Although CAF is a safe and predictable approach for root coverage (Pini Prato et al. 2018a), the application of this surgical technique in conjunction with autologous material (connective tissue graft) was reported to enhance the probability to achieve complete root coverage (CRC) in gingival recessions without interproximal attachment loss and non carious cervical lesions, with a long term stability (Chambrone et al. 2015, 2018; Pini Prato et al. 2018b).

Free gingival graft (FGG) technique has been confirmed as a valuable method to obtain newly created keratinized tissue stability up to 27 years (Agudio et al. 2009). However, since this technique uses epithelialized grafts, it generally results in compromised aesthetics (“patch-like area”). Alternatively, free connective tissue grafts (CTG) are used providing higher predictability and resulting in better colour matching (Chambrone et al. 2015, 2018; Pini Prato et al. 2018b). Unfortunately, both techniques are associated with a variable patient morbidity due to the wound at the palatal donor site and with the limited available amount of soft tissue.

As a consequence, part of the research in Mucogingival Surgery is now focusing its attention on the validity assessment of potential soft tissue substitutes in order to permit a their easier and broader use in reconstructive technique and avoiding limitations in the size, shape and homogeneous thickness of the alternative material. Several companies are offering in the market different quality of substitutes with different characteristics. As a consequence, several studies (Tonetti et al. 2018, Ahmedbeyli et al. 2014, Rotundo et al. 2012, Thoma et al. 2010) have been conducted in order to test them and to assess their efficacy and biological capability comparing with the gold standard approach represented by the use of a soft tissue autograft. For instance, there is evidence that the use of CAF with acellular dermal matrix (ADM) leads to a higher possibility of CRC achievement and thicker periodontal biotype changes (Chambrone et al. 2015, Ahmedbeyli et al. 2014). However, since the allograft material is derived from human cadavers, it is associated with ethical concerns and the risk of disease transmission. A recent systematic review and meta-analysis was aimed to compare clinical outcomes and width of keratinized tissue (KT) around teeth, following a soft tissue alternative (living cultured

cells) and FGG procedures. Data analyses showed that soft tissue alternatives resulted in an increased width of KT, but inferior (1.39mm) when compared with FGG (Dragan et al. 2017).

An option to avoid patient morbidity (due to donor sites) as well as the use of allograft material (with specific risk of transmission of human diseases) is the use of xenogenic collagen matrices (XCM). The suggested device is structured with a spongy portion (predominant) and a compact layer. The spongy part of the XCM is likely to allow for tissue ingrowth, which might improve blood vessel ingrowth, root attachment, gingival thickness and consequently improving predictability and the sustainment of recession coverage. Ghanaati et al. (2011) reported that the bilayered matrix elicits a favorable tissue reaction, demonstrates potential as a barrier for preferential tissue ingrowth, and achieves a desirable therapeutic result when applied in humans for soft tissue regeneration.

The use of XCM in the treatment of gingival recessions has shown promising results and considered to be a suitable substitute to the connective tissue graft (Sanz et al. 2009, Herford et al. 2010, Schmitt et al. 2013). A recent systematic review (Atieh et al. 2016) was aimed to evaluate the use of XCM in comparison with CTG, CAF and FFG for the treatment of gingival recessions and/or insufficient KT in terms of clinical parameters and patient- related outcomes. The conclusions based on the only 2 available studies at unclear risk of bias (Cardaropoli et al. 2014, Jepsen et al. 2013) showed that no evidence resulted to demonstrate the effectiveness of XCM in achieving greater root coverage, recession reduction and gain in KT compared to CTG plus CAF. Superior short-term results in treating root coverage compared with CAF alone were possible. In addition, there was limited evidence that XCM may improve aesthetic satisfaction, reduce postoperative morbidity and shorten the operating time.

Therefore, the aim of the present CONSORT-based randomized clinical trial is to test the adjunctive benefit of XCM to the CAF in terms of root coverage, KT augmentation and patient-reported outcomes.

## MATERIALS AND METHODS

### Trial design

This is a single-centre, superiority, double blind clinical trial, with balanced randomisation and parallel two groups design according to CONSORT statement (Schulz et al. 2010). Ethical approval was obtained by the competent local authority (Azienda USL 3 Pistoia, prot. 24/CESM 19.11.2012). All subjects will sign an informed consent and all study procedures will be performed according to the Declaration of Helsinki on experimentation involving human subjects.

### Participants

Patients will be recruited in a private office in Pistoia, Italy. All the recruited patients had to satisfy the following inclusion and exclusion criteria:

#### *Inclusion Criteria*

1. The patient (male or female) must be 18 years or older
2. Presence of gingival recessions in the upper jaw, involving teeth from central incisor to first molar
3. Gingival recessions on at least 2 adjacent teeth with a minimal depth of 2mm and detectable cemento-enamel junction (CEJ) (abrasion step <1mm)
4. The patient is able to comply with the study-related procedures such as exercising good oral hygiene and attending all follow-up procedures
5. Full Mouth Plaque (FMPS) and Bleeding (FMBS) Score <20%
6. The patient is able to fully understand the nature of the proposed surgery and is able to provide a signed informed consent

#### *Exclusion Criteria*

1. Smoker patients
2. Pregnant patients
3. Patients affect by uncontrolled diabetes

4. General contraindications for dental and/or surgical treatment are present
5. History of malignancy, radiotherapy, or chemotherapy for malignancy within the past 5 years
6. The patient is taking medications or having treatments which have an effect on mucosal healing in general (e.g. steroids, large doses of anti-inflammatory drugs, anticoagulation drugs)
7. The patient has a disease, which affects connective tissue metabolism (e.g. collagenases)
8. The patient is allergic to collagen
9. The patient is an abuser of alcohol or drug
10. Patients have participated in a clinical trial within the last six months
11. Presence of untreated periodontitis
12. Gingival recessions on molar teeth (excluding the first) or on malpositioned teeth
13. Presence of abrasion  $\geq 1$  mm or cervical restoration, with non-detectable CEJ

## **Intervention**

### *Pre-Surgical Phase*

All subjects will receive a full periodontal examination, with probing of pocket depth (PD), Full Mouth Plaque Score (FMPS) and Full Mouth Bleeding Score (FMBS). Prior surgical therapy, all patients will receive instructions on correct (atraumatic) domiciliar oral hygiene procedures, in order to avoid the persistency of wrong tooth cleaning habit and a course of professional oral hygiene procedure.

### *Surgical Procedure*

A single operator (RR) with more than 20 years of experience in mucogingival surgery will perform all surgical interventions. According to Zucchelli & De Sanctis (2000), an envelope split-full-split thickness flap without vertical incisions will be carried out. The horizontal incision will extend to include one tooth on each side of the teeth to be treated, in order to facilitate the planned coronal

repositioning of the flap tissue over the exposed root surfaces. The chronometer will start at the first incision. The oblique interdental incisions will be carried out keeping the blade parallel to the long axis of the teeth in order to dissect split-thickness the surgical papillae. Gingival tissue apical to the root exposures will be raised full-thickness in order to provide with more thickness that portion of the flap critical for root coverage. The most apical portion of the flap will be elevated split-thickness to facilitate its coronal displacement. Afterwards, the interdental papillae were de-epithelialized using a microscissor. The root surfaces will be mechanically treated with the use of curettes, avoiding the connective attachment area near the bone crest. A sharp dissection into the vestibular lining mucosa will be then carried out to eliminate muscle tension. Only at this point of the surgical procedure the envelope will be opened to allocate the patient to the treatment. In the test site the xenogenic collagen matrix (XCM)\* will be applied to all teeth with recession defect. The surgical technique employed in the test group consisted of the following additional steps:

1. After the preparation of the flap, the XCM will be cut into the right dimensions, measured with the probe, and its measurements recorded.
2. XCM will be placed from the CEJ to the bone crest on the recipient bed using single sutures, 7/0 PGA sutures.
3. The matrix will be rehydrated with blood, in order to reconstitute and maintain the maximal thickness possible.
4. The flap will be closed slightly coronal to the CEJ with a sling suture using resorbable PGA 6/0 sutures and avoiding any compression of the matrix.

In the control group, sling sutures will be performed to accomplish a precise adaptation of the buccal flap on the exposed root surfaces and to stabilize every single surgical papilla over the de-epithelialized anatomic papillae.

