## **Outcomes**

The objective of this RCT is to compare the coronally advanced flaps with a xenogeneic collagen matrix (test group) versus coronally advanced flaps alone (control group) in the treatment of multiple recession defects. In order to establish a superiority effect of the collagen matrix, the following endpoints will be considered:

*Primary Endpoint:* Mean recession reduction after 6 and 12 months post treatment

*Secondary Endpoints:*

- 1) Percentage of complete root coverage after 6 and 12 month
- 2) Thickness of soft tissue over the root after 6 and 12 month
- 3) Recession width after 6 and 12 month.
- 4) Keratinized Tissue (KT) width
- 5) Patients satisfaction

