### *Clinical Measurements*

For the assessment of the periodontal and marginal health status the following variables will be measured on mid buccal surface of the treated teeth by the calibrated blinded examiner, using a calibrated North Carolina University probe. The measures will be rounded to the nearest 0.5mm:

1. Distance between CEJ and the free gingival margin (*Rec depth*)
2. Distance between incisal margin to the free gingival margin (*IM-GM*)
3. *Recession width (Rec width)*, represented by the horizontal measurement of gingival recession at the CEJ level
4. *Bleeding on Probing (BOP)*, recording the presence/absence of bleeding after probing (Ainamo & Bay 1975)

5. *Plaque Index (PI)*, recording the presence/absence of plaque on tooth surface (Ainamo & Bay 1975)
6. *Probing Pocket Depth (PD)*, measured using a periodontal probe between GM and the end of the gingival sulcus
7. *Clinical Attachment Levels (CAL)*, calculated as PD+Rec depth
8. *Keratinized tissue (KTw) width*, assessed with the visual and functional method by means a probe as a distance between GM and mucogingival junction (MGJ)
9. *Keratinized tissue (KT thick) thickness*, measured by the use of a needle pierced through the center of a circular-shaped silicon marker of 3 mm in diameter. The edge of the marker (k-file nr. 10) will be positioned at the soft tissue margin providing a distance from the margin of 1.5 mm. The distance between the tip of the needle and the silicon marker will be assessed by the use of a magnifying glass and a Dentsply Maillefer silicon stops AO197 will be used. In addition, a digital calliper C041 0-150 mm (Kennon Instruments) with a sensibility of 0.01 mm will be used (da Silva et al. 2004; Santamaria et al. 2008)
10. Duration of the surgery (in minutes), where the chronometer started from the first incision and stopped at last suture.

The periodontal indexes will be measured before the surgery (baseline) and at the follow-up visits, 3, 6 and 12 month after the surgery.

Standardized photos will be taken at baseline, after flap elevation, after material application, after suturing, and at 7 and 14 days, 1, 3, 6 and 12 months post-op. All pictures will be taken always frontal and in profile.

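### Does giving a closing level and suture specification only for the test arm confound the matrix effect with flap position?

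*Combined protocol and SAP*

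**What the plan says.** Surgical Procedure describes one flap for every patient: an envelope flap from a cited published technique, coronal repositioning planned, papillae de-epithelialised, roots treated and muscle tension released. Then comes allocation: "Only at this point of the surgical procedure the envelope will be opened to allocate the patient to the treatment".

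The test arm follows under the words "The surgical technique employed in the test group consisted of the following additional steps". The last of its four steps is "The flap will be closed slightly coronal to the CEJ with a sling suture using resorbable PGA 6/0 sutures", and that sentence goes on to warn against compressing the matrix. For controls, "sling sutures will be performed to accomplish a precise adaptation of the buccal flap on the exposed root surfaces". The same sentence gives these sutures a second aim, which concerns the papillae: "to stabilize every single surgical papilla over the de-epithelialized anatomic papillae".

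Outcomes gives the purpose of the endpoints: "In order to establish a superiority effect of the collagen matrix". Clinical Measurements defines recession depth as "Distance between CEJ and the free gingival margin". It schedules probe readings at baseline and at 3, 6 and 12 months, and photographs at several points, including just after suturing. Blinding says that the surgeon knows the arm, while patients and outcome assessors do not.

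**The concern.** Three features together look like a confounder. The closing level is written for one arm only. It refers to the landmark from which the primary endpoint is measured. And it is carried out after the envelope is opened, by someone who knows the allocation.

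If the flap margin were left at a different height in the two arms and the difference lasted, randomisation would not help, because the difference arises afterwards. The blinded examiner would record it faithfully. The mixed model in Data analysis, with treatment, patient and baseline value, has no means of separating it from the matrix. No probe reading is planned between baseline and 3 months that would show where the margin stood at the end of surgery. At stake would be whether a significant result could be credited to the matrix alone.

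**Working it through.** **The plan's own figure.** Inputs from Sample Size: difference 1 mm, SD 0.93 mm, 2.92 teeth per patient, intraclass correlation 0.35, two-sided 5%, power 90%, drop-out 10%.

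- Sites per arm, ignoring clustering: 2 × [0.93 × (1.960 + 1.282) / 1]² = 18.18
- Design effect: 1 + (2.92 − 1) × 0.35 = 1.672
- Patients per arm: 18.18 × 1.672 / 2.92 = 10.41
- With drop-out: 10.41 / 0.9 = 11.56, rounded up to 12, as stated

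**How sensitive the comparison would be.** The SD of a patient mean is 0.93 × √(1.672 / 2.92) = 0.704 mm. The standard error (SE) of the difference is 0.704 × √(2/12) = 0.287 mm. Suppose the matrix does nothing and the arms differ by a lasting offset. The chance of a significant result, from a t-test with 22 df (critical value 2.074) and noncentrality offset/SE, is:

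| Assumed offset | Offset / SE | Two-sided rejection |
|---|---|---|
| 0 mm | 0 | 5.0% |
| 0.25 mm | 0.87 | 13.2% |
| 0.5 mm | 1.74 | 38.4% |

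With 11 per arm the SE is 0.300 mm, and the last two rates are 12.5% and 35.5%.

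Every offset in the table is an assumption. The 0.5 mm is the rounding step of the probe, not evidence about closure. The table also assumes that an offset at suturing survives in full to the endpoint visit, which nothing in the documents supports. So it answers how much an offset would matter, not whether there is one.

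**Whether the text gives reason to expect an offset.** Setting the two closure descriptions side by side:

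| Feature | Test | Control |
|---|---|---|
| Operator | same single, experienced surgeon | same |
| Flap technique and muscle release | common, before allocation | common, before allocation |
| Coronal repositioning over the exposed roots | planned | planned |
| Suture type | sling | sling |
| Closing level relative to the CEJ | stated | not stated |
| Suture material and gauge | stated | not stated |
| Papilla anchoring at closure | not repeated | stated |
| Matrix compression | to be avoided | not applicable |

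Each arm's closure text has details that the other lacks, which is what one expects when the same manoeuvre is described twice with different emphasis. The matrix clause is a good reason for describing closure again in the test list. The control sentence sets no competing level: it has the flap adapted to the exposed roots, and Surgical Procedure already plans coronal movement over those roots for everyone. The gap in suture specification is confined to material and gauge. No route from an unstated gauge to recession reduction is apparent from the documents, and Postoperative Care has all sutures out at 14 days.

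**The case for a change.** The best case for acting is that similar closure is plausible but not guaranteed. The common text gives a direction of movement, not an end point. The cited technique's own closure rule is not reproduced, and experience does not make an unblinded surgeon impartial. A list of additional steps can fairly be read to mean that its contents do not apply to controls. Remedies look cheap: one clarifying sentence, and a reading after the last suture of the incisal-margin measure, "Distance between incisal margin to the free gingival margin", which is already defined, is covered by the calibration and does not need a visible CEJ. That is about 24 × 2.92 = 70 readings.

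The reading of the text stands: the level, material and gauge are written for one arm only, and a reader cannot be certain of the intent for controls. The rest is weaker. An extra reading would have to be descriptive, since it falls after allocation and may be part of what the matrix itself does. A difference found there would not separate closure from matrix, and no planned result would change. It is also less cheap than it looks. Calibration session has one examiner take all measurements, and that examiner must stay blinded. The reading would bring the examiner into the operating session or fall to the surgeon, for whom no calibration is described. The photographs already planned after suturing give a rough check without that risk.

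**Conclusion.** No change to the plan follows. The protocol states some closure details for one arm and leaves them unstated for the other, but it does not prescribe different closures. Following it as written is not shown to give a wrong comparison. The sample size of 12 per arm reproduces and is unaffected.

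The potential size is bounded only by assumption. An offset would need to approach 0.5 mm, half the 1 mm target, and last to the endpoint visit to raise the false-positive rate to 38%. Nothing in the documents points to an offset of that size, or of either sign.

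The conclusion rests on reading the control sentence together with the common flap text, and on one operator working to one technique. If the investigators in fact intend different closures, the trial compares matrix plus closure method with flap alone, and the report should describe it so. Which level or suture is appropriate is a clinical matter on which no view is taken here.

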### **Postoperative Care and Measurement**

Following the surgery, patients will be instructed to rinse twice daily with chlorhexidine mouth rinse (0.12%) for 3 weeks. No toothbrushing will be allowed for 21 days, than they will be instructed to use an ultrasoft toothbrush. Anti-inflammatory therapy (Ibuprofen tablet, one before the surgery and one after 6 hours), antimicrobial therapy and additional analgesics will be prescribed according to the

---

\* Geistlich Mucograft®, Geistlich Pharma AG, Wolhusen, Switzerland

individual needs and the patient will be instructed to record daily the intensity of pain and the dose of medication in the patient questionnaire. All the sutures will be removed after 14 days.

## **Outcomes**

The objective of this RCT is to compare the coronally advanced flaps with a xenogeneic collagen matrix (test group) versus coronally advanced flaps alone (control group) in the treatment of multiple recession defects. In order to establish a superiority effect of the collagen matrix, the following endpoints will be considered:

*Primary Endpoint:* Mean recession reduction after 6 and 12 months post treatment

*Secondary Endpoints:*

- 1) Percentage of complete root coverage after 6 and 12 month
- 2) Thickness of soft tissue over the root after 6 and 12 month
- 3) Recession width after 6 and 12 month.
- 4) Keratinized Tissue (KT) width
- 5) Patients satisfaction

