### **Sample Size**

The following 2 hypothesis were considered: H0, where there is no difference in mean recession reduction between CAF+XCM and CAF alone; H1, where there is a difference in mean recession reduction between CAF+CM and CAF alone.

The following variables were used in order to calculate the sample size:

- Endpoint: Normal. Difference in reduction in gingival recession (root coverage) between baseline and 1 year
- Clinical important difference (Effect size d): set at 1 mm
- Assessing variability: From a previous study (Woodyard et al. 2004) in an envelope type of CAF for multiple recessions the standard deviation of recession reduction was 0.93 mm.
- Mean number of treated teeth per patient: from a previous study (Woodyard et al. 2004) it was 2.92
- Intraclass correlation coefficient (ICC) of the cluster sites (recessions nested into patient): from a previous study (Woodyard et al. 2004) it was 0.35
- Allocation ratio: 1:1
- Type I error:  $\alpha = 0.05$
- Type II error:  $\beta = 0.10$ , corresponding to a Power of 90%
- Accounting for drop-out: Anticipation of 10% of patient drop-out.

Based on this consideration and applying a formula for cluster design to detect a difference between treatments of 1 mm in recession reduction (standard deviation of 0.93 mm - Woodyard et al. 2004) with a two- side 5% significance level, a power of 90%, a mean number of treated teeth per patient

of 2.92, an intraclass correlation coefficient of 0.35, a sample size of 12 patients per treatment will be necessary.

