### **Data analysis**

Descriptive statistics will be performed using a mean and standard deviation for quantitative data and frequency and percentage for qualitative data. All unintentional side effects in each group will be reported. For quantitative variables mixed models will be performed with the treatment (CAF versus CAF+CM) as a fixed explicative variable and patient as a random variable. Baseline value will be used as a covariate. Interaction terms between treatment and the covariate will be used only if significant.

Complete root coverage will be analysed with a multilevel logistical model at two level (patient and tooth). For the patient-reported outcomes and experience measures t-tests will be applied. Estimates for the treatment effect, standard errors, p-values and 95% confidence intervals are provided. The statistical software will be MLwiN 2.21 Centre for Multilevel Modelling, University of Bristol.

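### The primary endpoint names both 6 and 12 months, the sample size covers one test at 1 year, and no rule says which visit decides superiority

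*Combined protocol and SAP*

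**What the plan says.** The Outcomes section introduces its list with "In order to establish a superiority effect of the collagen matrix, the following endpoints will be considered". The only primary entry is "Mean recession reduction after 6 and 12 months post treatment", which gives the two visits equal standing. Clinical Measurements schedules the periodontal measurements at baseline and at 3, 6 and 12 months, so both results will exist.

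The Sample Size section uses one time point. Its endpoint is "Difference in reduction in gingival recession (root coverage) between baseline and 1 year", planned with a "two- side 5% significance level, a power of 90"%. The hypotheses in the same section name no visit: "H0, where there is no difference in mean recession reduction between CAF+XCM and CAF alone", with H1 worded in parallel.

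The Data analysis section says that for quantitative variables "mixed models will be performed with the treatment (CAF versus CAF+CM) as a fixed explicative variable and patient as a random variable", with the baseline value as covariate. It mentions no visit term. It does not say whether one model is fitted or one per visit, which result is decisive, or how two results are combined.

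**The concern.** A superiority trial needs one decision rule for its primary claim, fixed before the data are seen. Here three rules are compatible with the text: success at 12 months alone, success at either visit, or success at both. They differ in type I error and in power, and the sample size was worked out for the first only.

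As written, the deciding visit could be chosen once the results are known. If the two visits disagreed, there would be no pre-specified answer to the trial's main question, and no later analysis could supply one.

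**Working it through.** **Inputs from the Sample Size section.** Difference 1 mm; SD 0.93 mm per tooth; 2.92 teeth per patient; intraclass correlation 0.35; two-sided alpha 0.05; power 90%; 1:1 allocation; 10% drop-out.

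**Step 1: reproduce the plan's figure.**

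- Design effect: 1 + (2.92 − 1) × 0.35 = 1.672
- Variance of a patient mean: 0.93² × 1.672 / 2.92 = 0.4952
- Patients per arm: 2 × (1.960 + 1.282)² × 0.4952 / 1² = 10.41
- With 10% drop-out: 10.41 / 0.9 = 11.56, so 12

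This matches the stated 12 per arm. The sample size is right for one test at one time point.

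**Step 2: power of that single test.** With 12 × 0.9 = 10.8 evaluable patients per arm, the standard error is √(2 × 0.4952 / 10.8) = 0.303. The standardised effect is 1 / 0.303 = 3.302. Power by the normal approximation is Φ(3.302 − 1.960) = 91.0%. With all 12 per arm it is 93.6%.

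**Step 3: two visits.** Let ρ be the correlation between the 6- and 12-month treatment estimates. The documents do not give it, so 0.5 to 0.9 is assumed. Treat the two test statistics as bivariate normal.

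- Either visit counts: type I error = 1 − P(both |Z| < 1.960), with no effect at either visit.
- Both required: power = P(both Z > 1.960). This also assumes the same 1 mm effect and SD at 6 months.
- Visits disagree: 2 × (single-test power − joint power), under the same assumption.

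| ρ | Either counts: type I error | Both required: power at 10.8 per arm | Both required: power at 12 per arm | Exactly one significant, 10.8 per arm |
|---|---|---|---|---|
| 0.5 | 9.1% | 84.8% | 88.9% | 12.4% |
| 0.7 | 8.3% | 86.1% | 89.8% | 9.8% |
| 0.8 | 7.8% | 87.0% | 90.5% | 8.1% |
| 0.9 | 7.0% | 88.2% | 91.4% | 5.7% |

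For example, at ρ = 0.5 the last column is 2 × (0.910 − 0.848) = 0.124.

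Outside this range, the either-visit error is 6.5% at ρ = 0.95. With independent tests, the upper case, it is 1 − 0.95² = 9.75%. A simulation with t-tests at 12 per arm gave 9.1% at ρ = 0.5 and 7.1% at ρ = 0.9, so the small sample does not alter the picture.

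**The case against.** The strongest reply is that the plan already points to 12 months. The sample-size endpoint is listed directly after H0 and H1 and names one time point, and 12 per arm reproduces on it. On that reading the error is 5%. Moreover, the endpoint joins the visits with a conjunction. If that means both are required, the error is at most 5%. The inflation arises under only one of three readings, and the plan does not state that reading.

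Part of this stands. The 7.0% to 9.1% is not the plan's error rate; it is what an either-visit rule would give. But the 1-year entry is a planning input, not a decision rule, and the section that defines the primary endpoint gives 6 months equal rank. The conjunctive reading does not reconcile the sections either, because the trial was not sized for joint success.

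Two points on the figures are fair. A higher correlation than 0.9 is plausible, since one examiner measures the same teeth, and it would shrink the inflation. The 91.0% for one test is a normal approximation: a two-sample t-test on patient means gives 88.0% at 10.8 per arm and 91.4% at 12, before any gain from the baseline covariate. So the contrast between one test above 90% and joint success below it depends partly on the formula. Neither point affects the missing rule.

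**Conclusion.** The concern holds, and it should be fixed before the results are known because it bears on the trial's one confirmatory claim. Two primary time points are set against a single 5% test sized at one of them, and no section reconciles the two.

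The consequence depends on the rule eventually applied:

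- **12 months alone:** the stated 5% holds, and so does the 90% on the plan's own formula.
- **Either visit:** the error exceeds 5% by 2.0 to 4.1 percentage points over the assumed correlations.
- **Both visits:** the error is at most 5%, but power is 2.8 to 6.2 points below that of the single test at 10.8 per arm (91.0% less 88.2% and 84.8%).

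The chance of discordant visits, 5.7% to 12.4%, is large enough to matter. It rests, as does the joint power, on an equal effect and SD at 6 months, which the plan does not state. That the deciding rule is absent rests on no assumption.

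**What to change.** In Outcomes, make mean recession reduction from baseline to 12 months the single primary endpoint and list the 6-month result among the secondary endpoints. In Data analysis, state that the two-sided 5% test of treatment at 12 months alone decides superiority. Naming 12 months in H0 and H1 would complete the link.

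The cost is one sentence in each of the two sections. The sample size stays at 12 per arm and no visit is added or dropped. The one downside is that a 6-month result on its own could no longer support the superiority claim.

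Other rules would also close the gap, but at a price. Requiring both visits lowers power as shown. Allowing either visit at 2.5% each raises the requirement to 12.29 patients per arm before drop-out, and 12.29 / 0.9 = 13.66, so 14 per arm.
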